14 ASSESSMENT OF SAFETY

14.1 Specifications of Safety Parameters

Pharmacokinetic analyses

Plasma concentrations of MF and cortisol at specified time points will be performed. Samples will be analyzed with a validated bioanalytical method for both human plasma MF with a lower limit of quantification (LLOQ) of 0.25 pg/mL and for cortisol with an LLOQ of 1.00 ng/mL. Additionally, measurement of urinary cortisol excretion 24 hours prior to the baseline procedure and 24 hours after the baseline procedure will be analyzed using a validated bioanalytical method with a LLOQ of 1.00 ng/mL.

Adverse event assessment

Adverse events (AE) for each subject from the time the subject gives informed consent through Day 30 in the PK cohort and through Day 60 in the randomized cohort (end of study) will be recorded in the EDC system and monitored. Each AE will be evaluated by clinical investigators in terms of strength of relationship (i.e., not related, unlikely related, probably related, definitely related) to study drug, study device, and dilation procedure. Each AE will be reviewed by sponsor personnel or contractors. The study sponsor is responsible for ensuring that all AEs are appropriately recorded and, when applicable, reported to the government(s), ethics committee(s) and other study centers per applicable regulations.

Subjects with CRS experience a persisting set of symptoms associated with the disease and may continue to present with a wide range of symptoms during the recovery process after in-office balloon dilation. These may include symptoms such as pain and discomfort, headache, decreased sense of smell, crusting, epistaxis, and other symptoms. Patients healing appropriately after in-office procedure may suffer from acute infections and/or inflammatory exacerbations unrelated to the procedure due to the natural course of their CRS. Therefore, clinical investigators will evaluate the occurrence of AEs excluding usual post-operative recovery signs and symptoms experienced by study subjects, unless corroborated by objective findings and/or requiring specific medical or therapeutic interventions (e.g., antibiotics, repeat ESS, etc.).

Note: The need for medical or surgical intervention in the FSO post-dilation that is captured on the endoscopic scoring CRF, will not be considered an AE. Likewise, other endoscopic findings such as adhesion/scarring, polyp formation and restenosis of the FSO will not be considered AE.

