Serious adverse event (SAE)	
Adverse events are considered “serious” if, in the view of either the investigator or sponsor, they result in any of the following outcomes:
 
 • Death; or • A life-threatening illness or injury; or • Permanent impairment of a body structure or a body function; or • Inpatient hospitalization or prolongation of existing hospitalization; or • Medical or surgical intervention to prevent life-threatening illness or injury or permanent impairment to a body structure or a body function; or • Fetal distress, fetal death, or a congenital anomaly/birth defect. 
Important medical events that may not result in death, be life-threatening, or require hospitalization may be considered serious when, based upon appropriate medical judgment, they may jeopardize the patient and may require medical or surgical intervention to prevent one of the outcomes listed in this definition. [BS EN ISO 14155]

Serious adverse device effect (SADE)	
Adverse device effect that has resulted in any of the consequences characteristic of a serious adverse event. Anticipated serious adverse

Term	Definition
	device effect (ASADE) is an effect which by its nature, incidence, severity or outcome has been identified in the risk analysis report.
Sino-Nasal Outcome Test (SNOT-22)	Validated, disease-specific, symptom-scoring instrument consisting of 22 questions, each scored by patient on a 6-point scale as follows: 0: No problem 1: Very mild problem 2: Mild or slight problem 3: Moderate problem 4: Severe problem 5: Problem as bad as it can be The maximum total score for all symptoms is equal to 110.
Source data	All information in original records and certified copies of original records of clinical findings, observations, or other activities in a clinical trial necessary for the reconstruction and evaluation of the trial.
Source documents	Original documents, data, and records. Printed, optical, or electronic documents containing source data.
Subject	An individual who participates in a clinical investigation.
Successful dilation of the FSO	Insertion of the UP Device into the targeted FSO followed by 2 consecutive complete inflations of the balloon.

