9.2.2 Secondary Endpoints

Endoscopic measures in the FSO by clinical investigators at specified timepoints through Day 30 in the PK cohort and through Day 60 in the randomized cohort:

- Estimated FSO diameter, smallest and largest (mm)
- Frequency and grade of patency (5-point categorical scale)
- Inflammation (0-100 scale)
- Frequency and severity of adhesion/scarring (4-point categorical scale)
- Frequency and grade of polypoid edema (4-point categorical scale)
Need for and frequency of post-dilation interventions (e.g., medical, repeat dilation, surgical)

Endoscopic endpoints in the FSO by independent reviewer in the randomized cohort:

- Estimated diameter, smallest and largest (mm) at Day 14 and Day 30
- Frequency and grade of patency at Day 14 and frequency of patency at Day 30 (5-point categorical scale)
- Inflammation (0-100 scale) at Day 14 and Day 30
- Frequency and severity of adhesion/scarring (4-point categorical scale) at Day 14 and Day 30
- Frequency and grade of polypoid edema (4-point categorical scale) at Day 14 and Day 30
- Need for and frequency of post-dilation interventions (e.g., medical, repeat dilation, surgical) at Day 14 and Day 30

Patient-reported outcomes (PK cohort only):

- Change from baseline to Day 14 and Day 30 in Sino-Nasal Outcome Test (SNOT-22) scores

See **Section 3 Definitions of Terms**.

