14.3 Guidelines for Reporting of Adverse Events

All AEs, regardless of seriousness or relationship to the investigational device and compatible accessory devices, will be recorded in the EDC system and will include event description, date of onset, investigator's assessment of severity, relationship to investigational device, and date of resolution/stabilization of the event. All AEs occurring while on study must be documented appropriately regardless of relationship. All AEs will be followed through end of the study.

Any pre-existing medical condition that is present at the time of screening will not be reported as an AE. The occurrence of diagnostic or elective surgical procedures for a pre-existing condition will not be recorded as an AE, unless the condition become more severe or results in an AE.

Whenever possible, diagnosis or single syndrome should be reported instead of symptoms. The investigator should specify the date of onset, severity, action taken with respect to the investigational or accessory device, corrective treatment/therapy given, additional investigations performed, outcome, and his/her opinion as to whether there is a reasonable possibility that the AE was caused by the investigational or accessory device.

The investigator should take appropriate measures to follow all AEs until resolution or until progression has been stabilized, or until study exit, to ensure the safety of the subjects. If the AE continues beyond the last planned visit per protocol and/or the subject withdraws from the study, clinical investigators should follow the subjects according to standard of care.

If a subject decides to withdraw from the study, clinical investigator should follow patients with ongoing AEs till resolution according to the standard of care.

All AEs must be reported to the sponsor based on the following timeline:

Type of Report	Reporting Schedule to the Sponsor
Investigational or accessory device-related AE	Verbal or written report within 10 working days
Patient death	Verbal report within 24 hours followed by a written report within 2 working days
SAE/SADE/UADE/USADE	Verbal report within 24 hours followed by a written report within 5 working days

Device malfunctions, device deficiencies and use errors must be reported to the sponsor promptly.

The investigator will report the above to the reviewing IRB per the IRB's guidelines. The study sponsor will be responsible for reporting safety events to the FDA as required per 21 CFR 812.

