15.1 Potential Risks

Risks associated with the use of the UP Drug-Coated Device are anticipated to be similar to those experienced by patients who undergo balloon dilation of the sinuses with a non-drug coated balloon.

Consequently, the risks potentially associated with the use of the UP Device may include but are not limited to the following:

- Epistaxis
- Cerebrospinal fluid leak
- Pneumocephalus
- Damage of the orbital wall or other ocular structures
- Impaired or loss of vision
- Impaired tearing
- Periorbital cellulitis/edema
- Infection
- Facial/nasal pain
- Facial/nasal discomfort
- Headache

Risks or side effects associated with intranasal mometasone furoate are:

- Nasal irritation
- Hypersensitivity reaction
- Intranasal bleeding (epistaxis)
- Localized infection (bacterial, fungal, or viral) in the nose or pharynx
- Nasal burning
- Nasal dryness
- Susceptibility to secondary infections
- Glaucoma/elevation of intraocular pressure
- Cataracts/change in lens opacities
- Headache
- Pharyngitis

Risks associated with steroids in general are:

- Alteration of the hypothalamic-pituitary-adrenal axis including growth suppression
- Immunosuppression
- Hypersensitivity reactions
- Headache
- Epistaxis
- Coughing
- Vomiting
- Candidiasis
- Glaucoma/elevation of intraocular pressure
- Cataracts/change in lens opacities
- Arthralgia
- Myalgia

Inhaled and intranasal MF is generally well tolerated in clinical trials and any AE are mild and generally of short duration with similar incidence to placebo. The proportion of patients discontinuing as a result of AEs related to treatment is very low and generally < 2-5% in most trials (Asmanex 2005; Dulera 2010; Nasonex 2005).

Intranasal glucocorticoids may occasionally cause local adverse effects, such as a mild sensation of nasal irritation, crusting, dryness, and usually minor epistaxis; however, these are transient and do not worsen during long-term treatment. Local mycotic infections and septal perforations with prolonged use of nasal corticosteroids are extremely rare and have not been reported for mometasone furoate. These findings may be related to the more rapid clearance of the topical corticosteroid by the ciliated nasal epithelium (Kyrizakis 2000; Van Cauwenbergh 2005; Vogt 1979).

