6.3.2 Randomized Cohort

All AEs reported by subjects between enrollment (i.e., consent date) and Day 60 follow-up visit (end of study) will be tabulated. Each AE will be evaluated by clinical investigators in terms of seriousness, severity (i.e., mild, moderate, severe) and strength of relationship (i.e., not related, unlikely related, probably related, definitely related) to study drug, study investigational device, study accessory device, and dilation procedure.

Device malfunctions and use errors will be reportable as applicable for both the investigational and the accessory devices.

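### The Note in protocol 14.1 takes FSO re-intervention and restenosis out of the AE definition with no exception for events that are serious

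*Protocol*

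**What the plan says.** The Note at the end of protocol 14.1 makes two exclusions. The first is that "The need for medical or surgical intervention in the FSO post-dilation that is captured on the endoscopic scoring CRF, will not be considered an AE". The second is that "other endoscopic findings such as adhesion/scarring, polyp formation and restenosis of the FSO will not be considered AE". The first applies only if the need is captured on the endoscopic form; the second has no condition. Neither mentions seriousness.

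The sentence just before the Note tells investigators to leave ordinary recovery symptoms out of AE assessment. It keeps those that have objective support or need treatment, and gives repeat ESS as an example of such treatment.

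Section 3 defines the AE broadly, with none of these exclusions. It defines an SAE as an AE with one of several outcomes. These include "Inpatient hospitalization or prolongation of existing hospitalization" and surgery to prevent permanent impairment.

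Section 14.3 says "All AEs occurring while on study must be documented appropriately regardless of relationship". It requires a verbal report of any SAE, SADE, UADE or USADE within 24 hours and a written one within 5 working days. Protocol 16.5 and SAP 10.7 tabulate AEs and SAEs, and SAP 6.3.2 says that "All AEs reported by subjects between enrollment (i.e., consent date) and Day 60 follow-up visit (end of study) will be tabulated".

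Re-interventions and restenosis are reported elsewhere. Protocol 16.6 and SAP 10.3.2.1 tabulate steroids and surgery given. Protocol 16.4 and SAP 10.4.2 compare need for intervention between sides, and SAP 10.4.2 does the same for stenosis or occlusion (patency grade 0 or 1).

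**The concern.** Safety is part of the study objective (protocol Section 8), and this is the first human study of the device (7.4). Keeping an efficacy outcome out of the AE tables is a defensible choice while the event is ordinary recurrence of the disease under study. It is harder to defend once the same event puts a subject in hospital.

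Without a seriousness exception, whether such an event is reported as an SAE depends on how the investigator reads one Note. An investigator following it literally would file no expedited report, severity grade or causality judgement. The SAE count would then partly reflect the definition rather than the device. The PK cohort success rule, which requires that no USADE occur (protocol 16.3, SAP 10.3.1), rests on the same definitions.

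**Working it through.** The point depends on no sample size, error rate or effect size, and the documents state no figure to reproduce. The check is to set the definitions side by side and follow one illustrative event through them.

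**Step 1. How the serious categories are built (Section 3).**
- SAE: an AE with a listed serious outcome.
- ADE: an AE related to use of the device.
- SADE: an ADE with a serious consequence.
- USADE: a SADE not identified in the risk analysis report.

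Each of the four starts from the AE. An occurrence that is not an AE enters none of them.

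**Step 2. The illustrative event.** Suppose a treated FSO restenoses, the investigator marks surgical intervention as needed on the endoscopic scoring form, and the subject is admitted for frontal re-operation.

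**Step 3. Is it an AE?** Under Section 3 alone, yes: it is an untoward medical occurrence, and the hospitalization criterion makes it serious. Under the Note, the restenosis is excluded as an endoscopic finding, and the need for surgery is excluded because it was captured on the form. Read literally, no AE remains unless the investigator records something separate, such as a symptom or a complication.

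**Step 4. Which outputs does it reach?**

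| Output | Literal reading of the Note |
|---|---|
| 24-hour SAE report (14.3) | Not triggered |
| Seriousness, severity and causality assessment (9.2.3, 14.1, 14.2) | Not required; called for only for AEs |
| AE/SAE tables (16.5, SAP 10.7) | Absent |
| Tabulation of interventions given (16.6, SAP 10.3.2.1) | Present |
| Need for intervention and stenosis by side (16.4, SAP 10.4.2) | Present if recorded at an analysed visit |

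**Step 5. Does another section restore it?** Section 14.2 classifies the relationship of AEs. Section 14.3 instructs that all AEs be recorded, which covers only what already qualifies as an AE. Protocol 16.5 and SAP 6.3.2 and 10.7 likewise work on AEs. None says that an excluded event becomes an AE when it is serious.

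**Step 6. Consistency within 14.1.** The sentence before the Note treats a symptom needing repeat ESS as an AE. The Note treats the need for surgery in the FSO as not an AE. For a symptomatic subject who needs repeat frontal surgery, the two give an investigator different starting points.

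**The case against.** The strongest reply is that nothing is hidden. FSO patency is the primary endpoint in the randomized cohort. Stenosis, scarring, polypoid edema and need for intervention are compared by side, at Days 14 and 30 by the independent reviewer and through Day 60 by investigators. Counting them again as AEs would duplicate them. This stands for ordinary events. For a serious one, the endpoint tables count sinuses or interventions and carry no seriousness, causality or reporting clock.

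Second, the Note excludes the need for intervention and the endoscopic finding, not a separate complication of the re-intervention. That stands, and it limits the gap.

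Third, the UADE is defined through serious adverse effects on health rather than through the AE, and 14.3 puts it on the 24-hour clock. That route is not clearly closed. It covers only device-associated effects that were not anticipated, however, and protocol 7.1 already describes ostial narrowing as a known response to dilation.

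Fourth, 14.3 exempts elective procedures for a pre-existing condition unless the condition worsens or leads to an AE, and bilateral FSO obstruction is an entry criterion. But that proviso qualifies its own exemption, not the Note. An ostium that returns to its entry grade has not become worse than at screening, and whether it leads to an AE returns the reader to the Note.

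Fifth, the repeat ESS wording can be reconciled if the symptom is the AE and the intervention is the endpoint. That is a reasonable reading, but the protocol does not state it.

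**Conclusion.** The Note is wrong as written, on a narrow point: it lacks an exception for seriousness, and no other section expressly supplies one. A serious FSO re-intervention or restenosis can therefore miss the 24-hour report and the AE/SAE tables while still being visible in the endpoint tables. This rests on a literal reading of the Note, on the intervention being captured on the endoscopic form, and on no separate AE being recorded. The documents give no rate from which to estimate how many of the 75 subjects might be affected.

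Three stronger readings are tempting, and the documents do not support them.
- A reader might infer that ordinary recovery symptoms are removed just as absolutely. They are not: 14.1 leaves them out "excluding usual post-operative recovery signs and symptoms experienced by study subjects, unless corroborated by objective findings" or treatment is required, which would retain most serious cases.
- A reader might infer that several risks named in 15.1 never reach the safety tables. Cerebrospinal fluid leak, orbital damage, vision loss and infection needing antibiotics are outside both exclusions. Epistaxis, headache and pain remain AEs when corroborated or treated.
- A reader might infer that every FSO-related admission is lost from the SAE count. The text shows only that one can be, given the separate-complication and UADE routes.

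Whether to log every untreated expected symptom is a matter of preference and is not part of this point.

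**What to change.** 1. Add a sentence to the Note in protocol 14.1: any intervention or endoscopic finding otherwise excluded here that meets a seriousness criterion in Section 3 is recorded as an AE/SAE and reported under 14.3.
2. Reconcile the Note with the repeat ESS wording before it, for example by stating that the symptom or clinical event is the AE while the intervention and the endoscopic grade are endpoints, subject to item 1.
3. In protocol 16.5 and SAP 10.7, cross-refer to the intervention tabulation in protocol 16.6 and the analyses in SAP 10.4.2, so that a reader of the safety results sees both.

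The cost is a short protocol amendment with matching SAP text, a few more SAE entries, and possibly a less favourable SAE count. Treatment, endpoints and sample size do not change.

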14.2 Classification of Adverse Events

All adverse events will be reported from the time of consent through study exit. The relationship of all AEs to the investigational device will be categorized into:

- *Definitely related*: There is a clear-cut temporal association, and no other possible cause.
- *Probably related*: There is a clear-cut temporal association, and a potential alternative etiology is not apparent.
- *Unlikely related*: The AE does not follow a reasonable temporal association; or causal relationship with the drug, device, or procedure involved in the research is unlikely but cannot be completely ruled out.
- *Not related*: The AE is completely independent of study product administration, and/or evidence exists that the event is definitely related to another etiology. There must be an alternative, definitive etiology documented by the investigator.

Any AE that is determined by a participating investigator to be related (definitely related, probably related) to the study drug, investigational device, accessory device or dilation procedure will be categorized as device-related.

For device-related AE (anticipated or unexpected/unanticipated), the sponsor may request source documentation to confirm the relationship of the AE to the investigational or accessory device and may review such AE with an independent otolaryngologist, as needed.

14.3 Guidelines for Reporting of Adverse Events

All AEs, regardless of seriousness or relationship to the investigational device and compatible accessory devices, will be recorded in the EDC system and will include event description, date of onset, investigator's assessment of severity, relationship to investigational device, and date of resolution/stabilization of the event. All AEs occurring while on study must be documented appropriately regardless of relationship. All AEs will be followed through end of the study.

Any pre-existing medical condition that is present at the time of screening will not be reported as an AE. The occurrence of diagnostic or elective surgical procedures for a pre-existing condition will not be recorded as an AE, unless the condition become more severe or results in an AE.

Whenever possible, diagnosis or single syndrome should be reported instead of symptoms. The investigator should specify the date of onset, severity, action taken with respect to the investigational or accessory device, corrective treatment/therapy given, additional investigations performed, outcome, and his/her opinion as to whether there is a reasonable possibility that the AE was caused by the investigational or accessory device.

The investigator should take appropriate measures to follow all AEs until resolution or until progression has been stabilized, or until study exit, to ensure the safety of the subjects. If the AE continues beyond the last planned visit per protocol and/or the subject withdraws from the study, clinical investigators should follow the subjects according to standard of care.

If a subject decides to withdraw from the study, clinical investigator should follow patients with ongoing AEs till resolution according to the standard of care.

All AEs must be reported to the sponsor based on the following timeline:

Type of Report	Reporting Schedule to the Sponsor
Investigational or accessory device-related AE	Verbal or written report within 10 working days
Patient death	Verbal report within 24 hours followed by a written report within 2 working days
SAE/SADE/UADE/USADE	Verbal report within 24 hours followed by a written report within 5 working days

Device malfunctions, device deficiencies and use errors must be reported to the sponsor promptly.

The investigator will report the above to the reviewing IRB per the IRB's guidelines. The study sponsor will be responsible for reporting safety events to the FDA as required per 21 CFR 812.

All SAEs (SAE/SADE/UADE/USADE) will be followed until satisfactory resolution; until the investigator deems the event to be chronic or the adherence to be stable or until the subject exits the study. Other supporting documentation of the event may be requested by the sponsor and should be provided as soon as possible.

All device deficiencies including malfunctions, use errors, and inadequate labeling, will be reported to appropriate regulatory bodies and Institutional Review Boards (IRBs)/Ethics Committees (ECs) as applicable.

Each AE will be coded using the Medical Dictionary for Regulatory Activities (MedDRA) and presented based on the system organ class and preferred term.

